## 12.2. Treatment Period (Days 1 [Baseline] to 168)

### 12.2.1. Visit 2 (Days 1 to 2)

#### 12.2.1.1. Day 1

The following procedures will be performed on Day 1 **before** the start of the study treatment infusion:

- Confirm all inclusion and exclusion criteria and confirm subject's eligibility for study participation.
- Record AEs and the status of unresolved AEs.
- Record concomitant medications.
- Conduct an abbreviated physical examination.
- Collect urine sample for urine pregnancy test (female subjects of childbearing potential only).
- Complete randomization procedure using IWRS schedule. Store randomization assigned in the Pharmacy Manual to prevent unblinding.
- [REDACTED]
- Collect blood for the following tests:
  - chemistry
  - hematology

- Administer premedications, if applicable (see Section 18.5).
- Measure vital signs (systolic and diastolic blood pressure, heart rate, respiration rate, and oral temperature) and SpO2 once before the study treatment infusion (if premedication is administered, vital signs should be measured after premedication).
- Administer assigned study treatment.

The following procedures will be performed on Day 1 **during** the study treatment infusion:

- Measure vital signs (systolic and diastolic blood pressure, heart rate, respiration rate, and oral temperature) and SpO2 **midinfusion  $\pm$  5 minutes** (if infusion is administered at a modified rate [REDACTED] the timing should correspond to the middle of the modified infusion duration).
- [REDACTED]

The following procedures will be performed on Day 1 **after** the end of the study treatment infusion:

- Measure vital signs (systolic and diastolic blood pressure, heart rate, respiration rate, and oral temperature) and SpO2 within 15 minutes after the end of the study treatment infusion.
- [REDACTED]

Refer to Section 18.6 for guidance on clinical trial conduct relating to COVID-19.

#### 12.2.1.2. Day 2

- Study personnel will call subjects not returning to the site to collect any AEs and concomitant medications that may have occurred after leaving the site on Day 1.

Refer to Section 18.6 for guidance on clinical trial conduct relating to COVID-19.

#### 12.2.2. Visit 3 (Day 15) All Subjects

Visit 3 will be conducted  $14 \pm 4$  days after the previous dose of study treatment. The following study procedures will be performed at Visit 3 **before** the study treatment infusion:

- Record AEs and the status of unresolved AEs.
- Record concomitant medications.

- Collect blood for the following tests:  
[REDACTED]  
[REDACTED]  
[REDACTED]

- Administer premedications, if applicable (see Section 18.5).
- Measure vital signs (systolic and diastolic blood pressure, heart rate, respiration rate, and oral temperature) and SpO2 once before the study treatment infusion (if premedication is administered, vital signs should be measured after premedication).
- Administer assigned study treatment.

The following study procedures will be performed at Visit 3 **during** the study treatment infusion:

- Measure vital signs (systolic and diastolic blood pressure, heart rate, respiration rate, and oral temperature) and SpO2 midinfusion  $\pm$  5 minutes (if infusion is administered at a modified rate [REDACTED] the timing should correspond to the middle of the modified infusion duration).

The following study procedures will be performed at Visit 3 **after** the study treatment infusion:

- Measure vital signs (systolic and diastolic blood pressure, heart rate, respiration rate, and oral temperature) and SpO2 within 15 minutes after the end of the study treatment infusion.

  
[REDACTED]

Refer to Section 18.6 for guidance on clinical trial conduct relating to COVID-19.

### 12.2.3. Visit 4 (Day 29) All Subjects

Visit 4 will be conducted  $14 \pm 7$  days after the previous dose of study treatment. The following study procedures will be performed at Visit 4 **before** the study treatment infusion:

- Record AEs and the status of previously unresolved AEs.
- Record concomitant medications.
- [REDACTED]
- Collect urine sample for urine pregnancy test (female subjects of childbearing potential only).
- Collect blood for the following tests:
  - chemistry
  - hematology

- Administer premedications, if applicable (see Section 18.5).
- Measure vital signs (systolic and diastolic blood pressure, heart rate, respiration rate, and oral temperature) and SpO2 once before the study treatment infusion (if premedication is administered, vital signs should be measured after premedication).
- Administer assigned study treatment.

The following study procedures will be performed at Visit 4 **during** the study treatment infusion:

- Measure vital signs (systolic and diastolic blood pressure, heart rate, respiration rate, and oral temperature) and SpO2 midinfusion  $\pm$  5 minutes (if infusion is administered at a modified rate [REDACTED] the timing should correspond to the middle of the modified infusion duration).

The following study procedures will be performed at Visit 4 **after** the study treatment infusion:

- Measure vital signs (systolic and diastolic blood pressure, heart rate, respiration rate, and oral temperature) and SpO2 within 15 minutes after the end of the study treatment infusion.
- Perform 12-lead ECG once, within 30 minutes after the end of the study treatment infusion.

[REDACTED]

Refer to Section 18.6 for guidance on clinical trial conduct relating to COVID-19.

#### 12.2.4. Visits 5, 7, 9, 11, and 13 (Days 43, 71, 99, 127, 155) All Subjects

Each of Visits 5, 7, 9, 11, and 13 will be conducted  $14 \pm 7$  days after the previous dose of study treatment. The following study procedures will be performed at these visits **before** the study treatment infusion:

- Record AEs and the status of previously unresolved AEs.
- Record concomitant medications.
- [REDACTED]
- Administer premedications, if applicable (see Section 18.5).
- Measure vital signs (systolic and diastolic blood pressure, heart rate, respiration rate, and oral temperature) and SpO2 once before the study treatment infusion (if premedication is administered, vital signs should be measured after premedication).
- Administer assigned study treatment.

The following study procedures will be performed at these visits **during** the study treatment infusion:

- Measure vital signs (systolic and diastolic blood pressure, heart rate, respiration rate, and oral temperature) and SpO2 midinfusion  $\pm$  5 minutes (if infusion is administered at a modified rate [REDACTED] the timing should correspond to the middle of the modified infusion duration).

The following study procedures will be performed at these visits **after** the study treatment infusion:

- Measure vital signs (systolic and diastolic blood pressure, heart rate, respiration rate, and oral temperature) and SpO2 within 15 minutes after the end of the study treatment infusion.

[REDACTED]

[REDACTED]

Refer to Section 18.6 for guidance on clinical trial conduct relating to COVID-19.

#### **12.2.5. Visits 6, 8, 10, and 12 (Days 57, 85, 113, and 141) All Subjects**

Each of Visits 6, 8, 10, and 12 will be conducted 14  $\pm$  7 days after the previous dose of study treatment. The following study procedures will be performed at these visits **before** the study treatment infusion:

- Record AEs and the status of previously unresolved AEs.
- Record concomitant medications.
- Collect urine sample for urine pregnancy test (female subjects of childbearing potential only)
- [REDACTED]
- Collect blood for the following tests:
  - chemistry
  - hematology

- [REDACTED]
- [REDACTED]
- [REDACTED]
- [REDACTED]
- [REDACTED]

- Administer premedications, if applicable (see Section 18.5).
- Measure vital signs (systolic and diastolic blood pressure, heart rate, respiration rate, and oral temperature) and SpO2 once before the study treatment infusion (if premedication is administered, vital signs should be measured after premedication).
- Administer assigned study treatment.

The following study procedures will be performed at these visits **during** the study treatment infusion:

- Measure vital signs (systolic and diastolic blood pressure, heart rate, respiration rate, and oral temperature) and SpO2 midinfusion  $\pm$  5 minutes (if infusion is administered at a modified rate [REDACTED], the timing should correspond to the middle of the modified infusion duration).

The following study procedures will be performed at these visits **after** the study treatment infusion:

- Measure vital signs (systolic and diastolic blood pressure, heart rate, respiration rate, and oral temperature) and SpO2 within 15 minutes after the end of the study treatment infusion.

Refer to Section 18.6 for guidance on clinical trial conduct relating to COVID-19.

### 12.3. End-of-Treatment (Visit 14 [Day 169]/Early Termination)

Visit 14/ET will be conducted  $14 \pm 7$  days after the final dose of study treatment. The following study procedures will be performed at this visit:

- Record AEs and the status of previously unresolved AEs.
- Record concomitant medications.
- Perform a complete physical examination, including weight.
- Perform a 12-lead ECG.
- Measure vital signs (systolic and diastolic blood pressure, heart rate, respiration rate, and oral temperature) and SpO2 before collection of blood samples.

- Collect urine sample for:
  - urinalysis
  - urine pregnancy test (female subjects of childbearing potential only)
- Collect blood for the following tests:
  - chemistry
  - hematology

Refer to Section 18.6 for guidance on clinical trial conduct relating to COVID-19.

## 12.4. Follow Up

### 12.4.1. Follow-Up Visit 1 (Visit 15/Day 197)

The FU visit will be conducted 4 weeks ( $\pm$  7 days) after Visit 14/ET (ie, 6 weeks [ $\pm$  7 days] after the final dose of study treatment). The following study procedures will be performed at this visit:

- Record AEs and the status of previously unresolved AEs.
- Record concomitant medications.
- Measure vital signs (systolic and diastolic blood pressure, heart rate, respiration rate, and oral temperature) and SpO2 before collection of blood samples.
- Collect urine sample for urine pregnancy test (female subjects of childbearing potential only)

Refer to Section 18.6 for guidance on clinical trial conduct relating to COVID-19.

### 12.4.2. Follow-Up Visit 2 (Visit 16/Day 239)

The second FU visit will be conducted 10 weeks ( $\pm$  7 days) after Visit 14/ET (ie, 12 weeks [ $\pm$  7 days] after the final dose of study treatment). The following study procedures will be performed at this visit:

- Record AEs and the status of previously unresolved AEs.
- Record concomitant medications.

- Measure vital signs (systolic and diastolic blood pressure, heart rate, respiration rate, and oral temperature) and SpO2 before collection of blood samples.

- Collect urine sample for:
  - urinalysis
  - urine pregnancy test (female subjects of childbearing potential only)
- Blood will be collected for the following tests:
  - chemistry
  - hematology

Refer to Section 18.6 for guidance on clinical trial conduct relating to COVID-19.

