**Table 1: Schedule of Events**

Visit	Screening a		Treatment Period						EOT	Follow-Up	
	1a	1b	2	3	4	5, 7, 9, 11, 13 (Simple tests)	6, 8, 10, 12 (Detailed tests)	14 (or ET)		15	16
Week	-6 to -1		0		2	4	6, 10, 14, 18, 22	8, 12, 16, 20	24 (2 wk postdose)	28 (4 wk post V14/ET)	34 (10 wk post V14/ET)
Study Day	-42 to -7		1	2	15	29	43, 71, 99, 127, 155	57, 85, 113, 141		169	197
Allowable Window (days) b					± 4	± 7	± 7	± 7	± 7	± 7	± 7
Study Procedure											
Informed Consent	X c										
Eligibility	X	X	X								
Demographics and baseline characteristics	X										
Medical history	X										
Adverse events	X d	X	X	X e	X	X	X	X	X	X	X
IPF history and previous treatments	X										
Prior medications	X										
Concomitant medications	X d	X	X	X e	X	X	X	X	X	X	X
Physical examination (complete)	X								X		
Physical examination (abbreviated) f		X	X								
Height	X										
Weight	X								X		
12-lead ECG	X	X				X g			X		
Vital signs h	X	X	X		X	X	X	X	X	X	X
Pulse oximetry: SpO 2 h	X	X	X		X	X	X	X	X	X	X
Chemistry	X		X		X			X	X		X
Hematology	X	X n	X		X			X	X	X n	X
Urinalysis	X								X		X
Pregnancy test (urine) for WCBP o	X		X		X			X	X	X	X
Serology (HCV Ab, HBsAg, HIV 1/2)	X										
SARS-CoV-2 test r	X										

Visit	Screening a		Treatment Period						EOT	Follow-Up	
	1a	1b	2	3	4	5, 7, 9, 11, 13 (Simple tests)	6, 8, 10, 12 (Detailed tests)	14 (or ET)	15	16	
Week	-6 to -1		0	2	4	6, 10, 14, 18, 22	8, 12, 16, 20	24 (2 wk postdose)	28 (4 wk post V14/ET)	34 (10 wk post V14/ET)	
Study Day	-42 to -7	1	2	15	29	43, 71, 99, 127, 155	57, 85, 113, 141	169	197	239	
Allowable Window (days) b				± 4	± 7	± 7	± 7	± 7	± 7	± 7	
Randomization			X								

Premedication (optional) w		X	X	X	X						
Study treatment		X	X	X	X	X	X				

Abbreviations: COVID-19 = coronavirus disease; ECG = electrocardiogram; EOT = end-of-treatment; ET = Early Termination; HBsAg = hepatitis B surface antigen; HCV Ab = hepatitis C virus antibody; HIV 1/2 = human immunodeficiency virus type 1 or 2; ICF = informed consent form; IPF = idiopathic pulmonary fibrosis; QC = quality control; SARS-CoV-2 = severe acute respiratory syndrome coronavirus 2; SOC = standard of care; V = Visit; WCBP = women of childbearing potential;

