#### **Male Subjects**

All males must agree to use a condom throughout the study and for 90 days after the last dose of study treatment to prevent seminal transmission of the IP.

In addition, males with female partners of childbearing potential must agree to use a highly effective method of contraception (see above) throughout the study and for 90 days after the last dose of study treatment.

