### **14.3. Exposure in Utero**

The subject will be instructed to notify the Investigator if the subject or subject's partner becomes pregnant during the study. The Investigator must notify the Sponsor within 24 hours, and must complete the Pregnancy Notification Form and submit it to the Sponsor within 2 working days of being notified. The Investigator should obtain informed consent/assent from the subject or subject's partner allowing the Investigator to obtain information regarding the pregnancy and its outcome. If the subject or subject's partner provides informed consent/assent, the Investigator should follow the pregnancy until outcome. A final Pregnancy Notification Form should be completed when the outcome of the pregnancy is known.

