### **14.5. Documentation of Adverse Events by Investigator**

Subjects will be evaluated and questioned generally to identify AEs during the course of the study. Adverse event collection will begin 24 hours before Visit 1a. Adverse events that occur up to and including 12 weeks after administration of the last dose of study treatment, including ET, must be reported.

All AEs spontaneously reported by the subject and/or in response to an open question from study personnel or revealed by observation, physical examination, or other diagnostic procedures will be recorded on the Adverse Event Form for that visit. Any clinically relevant deterioration in laboratory assessments, intercurrent illness, or other clinical findings is considered an AE and must be recorded on the Adverse Event Form. In addition, an abnormal test finding will be classified as an AE if one or more of the following criteria are met:

- The test finding is accompanied by clinical symptoms.
- The test finding necessitates additional diagnostic evaluation(s) or medical/surgical intervention; including significant additional concomitant drug treatment or other therapy. Note: simply repeating a test finding, in the absence of any of the other listed criteria, does not constitute an AE.
- The test finding leads to a change in study treatment dosing or discontinuation of subject participation in the clinical research study.
- The test finding is considered an AE by the Investigator.

Wherever possible, a specific disease or syndrome rather than individual associated signs and symptoms should be identified. However, if an observed or reported sign or symptom is not considered a component of a specific disease or syndrome by the Investigator, it should be recorded as a separate AE. Laboratory data will be collected as stipulated in this protocol. Clinical syndromes associated with laboratory abnormalities will be recorded as appropriate (eg, diabetes mellitus rather than hyperglycemia).

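### Visit 16 can fall 70 to 98 days after the final dose, not 77 to 91 as stated, so the last planned contact can precede the protocol's 12-week safety limit; pregnancy notification stops short of its 90 days

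*Protocol*

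**What the plan says.** **Visit timing.** Protocol 12.3 places Visit 14/ET 14 ±7 "days after the final dose of study treatment". Section 12.4.2 then says "The second FU visit will be conducted 10 weeks" (±7 days) after Visit 14/ET, and restates this in brackets as 12 weeks ±7 days after the final dose. Section 12.4.1 does the same for Visit 15: 4 weeks ±7 days after Visit 14/ET, restated as 6 weeks ±7 days after the final dose. Table 1 labels Visit 16 by its distance from Visit 14/ET only (week "34 (10 wk post V14/ET"), and SAP 2.2 and SAP Appendix 2 follow it.

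**Limits counted from the last dose.** Section 5.3 promises follow-up to 12 weeks after the last dose. Section 14.5 says: "Adverse events that occur up to and including 12 weeks after administration of the last dose of study treatment, including ET, must be reported". Section 14.6.1 sets the same 12 weeks for SAEs. The transplant-or-death endpoint (Protocol 13.1.2.1, SAP 7.5.2.5) runs to 12 weeks after the end of study treatment, a term that neither document defines.

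**End of observation.** No contact is scheduled after Visit 16, and Section 7.1 ends the trial at the last subject's last visit.

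**Pregnancy.** Section 10.3.2.3 requires men to use contraception "throughout the study and for 90 days after the last dose of study treatment"; for women the period is study follow-up or 90 days. On notification, Section 14.3 says: "The subject will be instructed to notify the Investigator if the subject or subject's partner becomes pregnant during the study". Inclusion criterion 15 (Synopsis and Section 8.1) limits partner pregnancies to the time of study participation.

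**The concern.** The protocol measures its safety follow-up from the last dose but schedules the visit that closes it from Visit 14/ET, which has its own window. The bracketed equivalence in 12.4.2 treats the two anchors as interchangeable and so hides how early the last visit may fall. A site can comply with Table 1 and still miss the stated limit from the final dose.

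At stake is active ascertainment at the end of the declared safety window. In a subject who attends early but within window, nobody is scheduled to ask about AEs, SAEs or transplants in the remaining days. The pregnancy issue is separate: the protocol imposes precautions for 90 days after the last dose but asks to be told of pregnancies only during the study, so it gives no instruction for a pregnancy recognised between the last visit and day 90.

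**Working it through.** **Inputs.** Visit 14/ET: 14 ±7 days after the final dose (12.3). Visit 15: 28 ±7 days after Visit 14/ET (12.4.1). Visit 16: 70 ±7 days after Visit 14/ET (12.4.2). Calendar days in Table 1: last dose Day 155 ±7, Visit 16 Day 239 ±7. Limits: 84 days (5.3, 14.5, 14.6.1) and 90 days (10.3.2.3).

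**1. The plan's own figure.** The centre reproduces: 14 + 70 = 84 days = 12 weeks, and 239 − 155 = 84. The stated tolerance gives 84 − 7 = 77 to 84 + 7 = 91.

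**2. Adding the windows.**
- Visit 16: earliest 7 + 63 = 70, latest 21 + 77 = 98.
- Visit 15: earliest 7 + 21 = 28, latest 21 + 35 = 56, against the stated 42 ±7 = 35 to 49.
- Cross-check for Visit 16 from Table 1: (239 − 7) − (155 + 7) = 232 − 162 = 70, and (239 + 7) − (155 − 7) = 246 − 148 = 98.

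The tolerance from the final dose is therefore ±14 days. The stated ±7 holds only if it is a second, independent constraint.

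**3. Gap to the 84-day limit.** Windows added: 84 − 70 = 14 days at most. Stated window binding: 84 − 77 = 7 days at most. Both readings leave a gap.

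**4. How often.** The documents give no distribution of attendance. Assume, for illustration, that each permitted day is equally likely and the two windows are independent.

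| Reading | Before day 84 | Before day 90 |
|---|---|---|
| Windows added (70–98) | 105/225 = 47% | 180/225 = 80% |
| Stated window binds (77–91) | 7/15 = 47% | 13/15 = 87% |
| Windows added, each visit kept within ±3 days | 43% | 98% |

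With the windows added, the shortfall against day 84 averages 560/105 = 5.3 days among those seen early and 560/225 = 2.5 days over all subjects.

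**5. Transplant limit.** If the end of study treatment means the last dose, the gap is as in step 3. If it means Visit 14, Visit 16 falls 63 to 77 days later and always precedes the 84-day limit.

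**6. Pregnancy.** A subject exactly on schedule has the last visit at day 84, and 90 − 84 = 6 days of the contraception period remain. At the earliest permitted visit, 90 − 70 = 20 days remain.

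**7. COVID-19 schedule.** Section 18.6.2.3 lets Visit 14 be up to 8 weeks (56 days) after the last dose, with Visit 16 10 ±1 weeks later: up to 56 + 77 = 133 days. The 98-day maximum is that of the standard schedule only.

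**The case against.** The strongest reply is that this is a wording slip with little consequence. Much of that reply stands.

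- **Adding the windows does not cause most of the early visits.** A reader might infer that the ±14-day range explains why about half of visits precede day 84. Step 4 shows otherwise: the stated window gives the same 47%, and a higher share before day 90. Both come from a symmetric window centred on day 84. Adding the windows only raises the maximum gap from 7 to 14 days.
- **The primary endpoint is not touched.** Safety is the primary objective, so it is tempting to say the primary analysis is weakened. Both primary endpoints rest on TEAEs, which close 2 weeks after the last dose (Protocol 14.2.1, SAP 3.4.6). Events starting on days 70 to 84 would be listed under SAP 7.6.2, not counted as TEAEs.
- **Reporting does not stop at Visit 16.** Sections 14.5 and 14.6.1 run to 12 weeks whatever the visit date, and spontaneous reports count.
- **The SAP provides for short follow-up.** In the time-to-event analysis of transplant or death, SAP 7.5.2.5 censors at 12 weeks or the last known alive date, whichever is earlier.
- **No pregnancy test at day 90 is promised.** The 90 days bind the subject, so the documents do not support calling the last test date a breach.

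Three things survive. The equivalences in 12.4.1 and 12.4.2 are arithmetically wrong unless read as extra constraints. On every reading of the standard schedule the last planned contact may precede the 12 weeks that Section 5.3 promises, and neither a continuing duty to report nor censoring recovers events that nobody asks about. And notification ends before the period for which the protocol requires precautions.

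**Conclusion.** The point holds as an inconsistency in late safety follow-up, and it is modest in size. On the standard schedule Visit 16 can fall 70 to 98 days after the final dose (stated: 77 to 91) and Visit 15 28 to 56 days (stated: 35 to 49). The last scheduled contact can precede the 12-week limit by up to 14 days if the windows add, or 7 if the stated tolerance binds. These ranges follow from the protocol's own figures; the percentages in the working rest on an assumed attendance pattern and are illustrative.

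The effect falls on AEs and SAEs late in the reporting window and on one secondary endpoint, whose limit is also unclear because the end of study treatment is undefined. A reader might infer that the primary safety comparison is compromised or that safety reporting lapses at Visit 16. The documents support neither.

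The pregnancy gap is separate and does not depend on the windows: at least 6 days for a subject exactly on schedule. It rests on reading the study in 14.3 as the subject's own participation, which is how inclusion criterion 15 words it for partners.

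**What to change.** 1. Correct the bracketed equivalences in Protocol 12.4.1 and 12.4.2, or state explicitly that they are additional limits.
2. Reconcile Table 1, Sections 12.3, 12.4.2, 14.5 and 14.6.1, SAP 2.2 and SAP Appendix 2 so that the last scheduled safety contact does not precede the protocol's own 12-week limit. Include Section 18.6.2.3 in the same pass: simply re-anchoring Visit 16 to the final dose could conflict with the COVID-19 provisions, which count it from a Visit 14/ET that may be much later.
3. Define the end of study treatment for the transplant-or-death endpoint in Protocol 13.1.2.1 and SAP 7.5.2.5.
4. Align the notification period in Section 14.3, and the partner wording in inclusion criterion 15, with the protocol's own 90 days after the last dose.

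The cost is amendment wording, plus a last contact up to 2 weeks later for subjects who would otherwise attend early. The sponsor should choose the form and window of that contact.
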